### **7.4.3 Other biomarkers**

Not applicable.

## **7.5 Safety evaluation**

The assessment of safety will be based on the frequency of adverse events, laboratory values that fall outside the pre-determined ranges, vital signs, as well as ECG data.

### **7.5.1 Adverse events (AEs)**

All information obtained on adverse events will be displayed by patient.

The number and percentage of subjects with adverse events will be tabulated by system organ class and preferred term. A subject with multiple adverse events within a body system is only counted once towards the total of this body system if no change in severity.

#### **7.5.1.1 Coding of AEs**

Adverse events are coded using the Medical Dictionary for Regulatory Activities (MedDRA) terminology. The latest version at the time of database lock will be used.

#### **7.5.1.2 Grading of AEs**

AEs will be graded according to the NCI Common Terminology Criteria for Adverse Events (CTCAE) version 4.0 (<http://ctep.cancer.gov/forms/CTCAEv4.pdf>).

The CTCAE represents a comprehensive grading system for reporting acute and late effects of cancer treatments. CTCAE v4.0 is graded by definition a 5-point scale generally corresponding to clinical severity (mild, moderate, severe, life-threatening, and death). This grading system

inherently places a value on the importance of an event although there is not necessarily proportionality among grades (a Grade 2 is not necessarily twice as bad as a Grade 1).

For adverse events for which CTCAE grades are not available, grades 1 – 4 corresponding to the severity of mild, moderate, severe, and life-threatening will be used. CTCAE grade 5 (death) is not used in this study. Information regarding death will be collected in the “Study Phase Completion Evaluation” CRF pages.

### 7.5.1.3 General rules for AE reporting

AE summaries will include all AEs starting on or after study day 1 (i.e. on or after the day of the first administration of study drug) and ending no later than 28 days after last study treatment or the follow-up visit, whichever is later. All AEs before data cutoff date will be listed, including those that start before study day 1. AEs starting prior to study day 1 will be identifiable based on the AE start date displayed in the listings.

AEs will be summarized by presenting the number and percentage of patients having at least one AE, and having at least one AE in each body system/primary system organ class and for each preferred term using the most current MedDRA coding available prior to database lock. A subject with multiple occurrences of an AE will be counted only once in the AE category. Separate AE summaries will be presented by primary system organ class, preferred term, and maximum CTC grade. A patient with multiple CTC grades for an AE will be summarized under the maximum CTC grade recorded for the event. In the summaries presented by grade, all AEs will be pooled regardless of whether they are CTC gradable or not. AEs with missing CTC grade will be summarized under “missing”.

Any information collected (e.g. CTC grades, relationship to study drug, action taken etc.) will be listed as appropriate.

For the legal requirements of ClinicalTrials.gov and EudraCT, two required tables on on-treatment adverse events which are not serious adverse events with an incidence greater than 5% and on-treatment serious adverse events and SAE suspected to be related to study treatment will be provided by system organ class and preferred term on the safety set population.

If for the same patient, several consecutive AEs (irrespective of study treatment causality, seriousness and severity) occurred with the same SOC and PT:

- a single occurrence will be counted if there is  $\leq 1$  day gap between the end date of the preceding AE and the start date of the consecutive AE
- more than one occurrence will be counted if there is  $> 1$  day gap between the end date of the preceding AE and the start date of the consecutive AE

For occurrence, the presence of at least one SAE / SAE suspected to be related to study treatment / non SAE has to be checked in a block e.g., among AE's in a  $\leq 1$  day gap block, if at least one SAE is occurring, then one occurrence is calculated for that SAE.

The number of deaths resulting from SAEs suspected to be related to study treatment and SAEs irrespective of study treatment relationship will be provided by SOC and PT.

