6.3 Patient demographics/other baseline characteristics

Demographics

Patient demographic and baseline characteristic data to be collected on all patients include: date of birth, sex, race, predominant ethnicity.

Relevant medical history / current medical conditions

Relevant medical history and current medical conditions will be recorded on the in the CRF until the start of the study drug.

Where possible, diagnoses and not symptoms will be recorded. Cushing's disease history together with the medication/treatment used will be collected.

Any event or change in the patient's condition or health status occurring **prior to** the initial study drug administration will be reported in the Relevant medical history/Current medical conditions section of the CRF.

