7.1 Adverse events

An adverse event is the appearance or worsening of any undesirable sign, symptom, or medical condition occurring after obtaining informed consent even if the event is not considered to be related to study drug. Study drug includes the investigational drug under evaluation and the comparator drug or placebo that is given during any phase of the study. Medical conditions/diseases present before obtaining informed consent are only considered adverse events if they worsen. Abnormal laboratory values or test results constitute adverse events only if they induce clinical signs or symptoms, or are considered clinically significant, or require therapy.

The occurrence of adverse events should be sought by non-directive questioning of the patient at each visit during the study. Adverse events also may be detected when they are volunteered

by the patient during or between visits or through physical examination, laboratory test, or other assessments. All adverse events must be recorded on the Adverse Events e(CRF) with the following information:

1. the severity grade CTC grade 1 – 4.
2. its relationship to the study drug(s) (suspected/not suspected).
3. its duration (start and end dates or if continuing at final exam).
4. whether it constitutes a serious adverse event (SAE).

An SAE is defined as an event which:

[figure not shown]
- is fatal or life-threatening.
- results in persistent or significant disability/incapacity.
- constitutes a congenital anomaly/birth defect.
- requires inpatient hospitalization or prolongation of existing hospitalization, unless hospitalization is for:
 - routine treatment or monitoring of the studied indication, not associated with any deterioration in condition.
 - elective or pre-planned treatment for a pre-existing condition that is unrelated to the indication under study and has not worsened since the start of study drug.
 - treatment on an emergency outpatient basis for an event not fulfilling any of the definitions of a SAE given above and not resulting in hospital admission.
 - social reasons and respite care in the absence of any deterioration in the patient's general condition.
- is medically significant, i.e. defined as an event that jeopardizes the patient or may require medical or surgical intervention to prevent one of the outcomes listed above.

Unlike routine safety assessments, SAEs are monitored continuously and have special reporting requirements; see [Section 7.2](#).

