All adverse events should be treated appropriately. Treatment may include one or more of the following: no action taken (i.e. further observation only); study drug dosage adjusted/temporarily interrupted; study drug permanently discontinued due to this adverse event; concomitant medication given; non-drug therapy given; patient hospitalized/patient's hospitalization prolonged. The action taken to treat the adverse event should be recorded on the Adverse Event e(CRF).

Once an adverse event is detected, it should be followed until its resolution or until it is judged to be permanent, and assessment should be made at each visit (or more frequently, if necessary) of any changes in severity, the suspected relationship to the study drug, the interventions required to treat it, and the outcome.

Information about common side effects already known about the investigational drug can be found in the Investigator Brochure (IB) or will be communicated between IB updates in the form of Investigator Notifications. This information will be included in the patient informed consent and should be discussed with the patient during the study as needed.

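### SAP 7.5.1.3 selects adverse events by start date alone, so whether an event that began before Day 1 and worsens on LCI699 is counted depends on a recording rule that neither document settles

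*SAP*

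**What the plan says.** **Selection.** SAP 7.5.1.3 sets the lower bound of the summaries as "AE summaries will include all AEs starting on or after study day 1" and the upper bound as "ending no later than 28 days after last study treatment or the follow-up visit, whichever is later". Events before the lower bound are shown but not tabulated: "All AEs before data cutoff date will be listed, including those that start before study day 1". There is no clause for an event that starts earlier and then worsens. Protocol 9.5.3 describes the tabulation without any Day 1 bound, so the filter comes from the SAP.

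**Definition.** Protocol 7.1 reads: "An adverse event is the appearance or worsening of any undesirable sign, symptom, or medical condition occurring after obtaining informed consent". For conditions that predate consent it adds: "Medical conditions/diseases present before obtaining informed consent are only considered adverse events if they worsen". Once detected, an event is followed to its end, and "assessment should be made at each visit (or more frequently, if necessary) of any changes in severity".

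**Grading.** SAP 7.5.1.3 says: "A patient with multiple CTC grades for an AE will be summarized under the maximum CTC grade recorded for the event".

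**Pre-dose events.** Protocol 6.3 gives a different destination. It says that an event or change in health "occurring prior to the initial study drug administration will be reported in the Relevant medical history/Current medical conditions section of the CRF".

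**The concern.** The protocol's definition has two limbs, appearance and worsening. The SAP's filter tests only when an event appeared. An event that opens during washout at grade 1 and reaches grade 3 on LCI699 is an on-drug change in safety status, but if it keeps its pre-dose start date it contributes to no percentage.

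This matters here for two reasons. The trial has a single arm and, by SAP 3, the Final CSR concentrates on long-term safety and efficacy, so these tables are a main output. The other safety outputs also compensate only in part. Shift tables cover laboratory values, vital signs and ECG (SAP 7.5.2 to 7.5.4). They do not cover clinical events such as fatigue, nausea, acne or hirsutism, which Protocol 3.5 discusses among the risks.

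**Working it through.** The plan states no figure on this point, so there is none to reproduce. The check applies the SAP filter to one constructed event under each recording practice that the documents allow, and then gives the scale.

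**Inputs**
- Filter: start day ≥ 1 (SAP 7.5.1.3), where Day 1 is the first dose (SAP 8.1).
- Pre-dose collection: screening runs from 74 to 15 days before Day 1, with consent before any procedure (Protocol 6.1). Up to 60 days of screening allow for washout (Protocol 3.1).
- Denominators: 19 patients enrolled under Amendment 4 (rationales of Amendments 6 and 9), assuming that all were dosed, and 15 as the planned expansion cohort (SAP 4 and 6).
- Constructed event: starts on Day -20 at grade 1 and rises to grade 3 on Day 10.

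**Step 1: apply the filter**

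| Practice | AE record(s) | Start ≥ 1? | In the summaries |
|---|---|---|---|
| A. One record follows the event | Day -20, maximum grade 3 | -20: no | 0 events, listing only |
| B. Worsening opens a new record | Day -20 to 9, grade 1; from Day 10, grade 3 | -20: no; 10: yes | 1 event, grade 3 |
| C. Pre-dose event in medical history, worsening entered as an AE | from Day 10, grade 3 | 10: yes | 1 event, grade 3 |

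The same clinical course gives 0 or 1 according to how it was entered.

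**Step 2: which practice do the documents prescribe?**
- Towards A: Protocol 7.1 counts events from consent and follows changes in severity on an event already detected. SAP 7.5.1.3 expects AE records with a start before Day 1.
- Towards B: SAP 7.5.1 counts a patient once per body system only when severity has not changed. The consecutive-event rule in SAP 7.5.1.3 foresees back-to-back records of one term, whatever their severity.
- Towards C: Protocol 6.3 sends pre-dose events to medical history. Protocol 6.6.1 does the same for significant examination findings, and sends later findings that meet the AE definition to the AE screen.

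No passage ranks these, and none says whether a grade change opens a new record.

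**Step 3: the disclosure tables.** Under B the gap between the two records is 10 - 9 = 1 day. The consecutive-event rule merges same-term records with a gap of at most 1 day, so they form one occurrence. The SAP does not say whether that block starts on Day -20 or Day 10, and it does not define on-treatment for these tables.

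**Step 4: scale.** With x patients counted out of N, the percentage is 100x/N (exact 95% interval in brackets).
- N = 19: 0/19 = 0% (0 to 17.6); 1/19 = 5.3% (0.1 to 26.0).
- N = 15: 0/15 = 0% (0 to 21.8); 1/15 = 6.7% (0.2 to 31.9).

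The registry table of non-serious events has a threshold of more than 5%. If it uses the same filter, one patient decides whether a preferred term appears, because 1/19 exceeds 5% and 0/19 does not.

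**The case against.** The strongest reply is that exclusion needs a premise that the documents do not supply, namely that worsening stays on the record opened before Day 1. Protocol 7.1 makes worsening an adverse event in its own right, and Protocol 6.3 and 6.6.1 keep pre-dose findings out of the AE pages. The sentence on multiple grades in SAP 7.5.1.3 can be read as a patient-level rule that collapses several records of a term. It need not mean one record carrying several grades. This stands. A reader might infer that such events are never counted, and the documents do not support that: under practices B and C they are.

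Three further inferences also fail.
- That overall incidence is understated. A patient with any other on-treatment event is still counted there, and all 11 patients in the preliminary data had at least one event (Protocol 1.1.1.3).
- That the patients affected are mainly those taken off effective drugs. Protocol 3.5 expects washout patients to be those whose current drug is failing or poorly tolerated.
- That events are hidden. All are listed with start dates, and with 19 patients a listing can be read case by case.

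The reply does not close the gap. SAP 7.5.1.3 itself anticipates AE records that start before Day 1, and Protocol 7.1 conflicts with 6.3 on where such events belong. A listing feeds no percentage.

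**Conclusion.** The point holds conditionally. The SAP's start-date rule implements only part of the protocol's definition of an adverse event. An event open at Day 1 that rises in grade on LCI699 is left out of the incidence and maximum-grade summaries if the rise stays on the same record, and counted otherwise.

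The number of patients affected is unknown. It is zero if no such event occurred, if pre-dose events were held as medical history, or if every worsening was entered separately. The scale of 5.3 points (of 19) or 6.7 points (of 15) per patient applies to a single preferred term or grade. It assumes that the patient has no other qualifying record of that term, and for the grade table none at the same or a higher grade. The effect on the registry tables further assumes that they share the filter. The rule is worth changing because the count should not depend on how a site happened to enter the event.

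**What to change.** In SAP 7.5.1.3, replace the start-date rule with wording such as:

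> The summaries include events with onset on or after study day 1, and events with earlier onset whose CTC grade increases, or which become serious, on or after study day 1. The latter are counted from the date, and at the grade, of the worsening.

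Apply the same rule to the disclosure tables, define on-treatment there, and say how a same-term block that straddles Day 1 is handled. State in the SAP which recording practice was used for pre-dose events that worsened, so that Protocol 6.3 and 7.1 can be read together.

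The cost is the SAP wording, one derivation (last pre-dose grade against maximum grade on treatment) and a check of the AE records open at Day 1 in about 19 patients. Where a record does not date its grade change, that check may need a site query. Some percentages may become slightly less favourable. If every worsening already has its own record, the incidence and maximum-grade results do not change.

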7.2 Serious adverse event reporting

To ensure patient safety, every SAE, regardless of suspected causality, occurring after the patient has provided informed consent and until 28 days after the patient has stopped study participation (defined as time of last dose of study drug taken or last visit whichever is later) must be reported to Novartis within 24 hours of learning of its occurrence.

Any SAEs experienced after this 28 day period should only be reported to Novartis if the investigator suspects a causal relationship to the study drug.

Recurrent episodes, complications, or progression of the initial SAE must be reported as follow-up to the original episode, regardless of when the event occurs. This report must be submitted within 24 hours of the investigator receiving the follow-up information. An SAE that is considered completely unrelated to a previously reported one should be reported separately as a new event.

Information about all SAEs is collected and recorded on the Serious Adverse Event Report Form. The investigator must assess the relationship of any SAE to study drug, complete the SAE Report Form in English, and send the completed, signed form by fax within 24 hours to the local Novartis Drug Safety and Epidemiology Department. The telephone and telecopy number of the contact persons in the local department of Clinical Safety and Epidemiology, specific to the site, are listed in the investigator folder provided to each site. The original copy of the SAE Report Form and the fax confirmation sheet must be kept with the case report form documentation at the study site.

Follow-up information is sent to the same person to whom the original SAE Report Form was sent, using a new SAE Report Form stating that this is a follow-up to the previously reported SAE and giving the date of the original report. The follow-up information should describe whether the event has resolved or continues, if and how it was treated, whether the blind was broken or not, and whether the patient continued or withdrew from study participation.

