### 3 Objectives

The primary objective of this study as well as several other objectives related to the safety and efficacy of 10-week and 22-week treatment of LCI699 have already been analyzed for the PoC cohort and described previous CSRs. For the sake of completeness, the objectives of the protocol (up to and including Amendment 9) are listed below.

The Final CSR will concentrate on reporting long-term safety and efficacy of osilodrostat in patients with Cushing's disease, [REDACTED]. For the assessment of efficacy, the analyses given for the secondary objectives will form the basis of the assessments. For each objective listed below it is indicated if this will be included in the Final CSR analyses.

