### 6.3 Imputation rules of partial or missing dates

Partial dates will remain partial in the data listing. For the purpose of analysis, the following imputation rules will be used to impute the partial dates: if the day and month is missing, it will be replaced by 30th June (to be used only for prior events, e.g. medical history); if only the day is missing it will be replaced by the 15th of that month. For the dates known to be within the trial period, if this imputation make the date later then the trial completion date, use the trial completion date; if the imputed date is earlier then the first medication date, use the first medication date.

The imputation of partial date for AE and concomitant medication will follow Novartis standard rules (See module 8 for details).

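### The SAP closes the AE summary window on the event's end date, so late-resolving AEs drop out of the incidence tables and ongoing AEs have no rule

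*SAP*

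**What the plan says.** **Summary window.** SAP 7.5.1.3 opens with "AE summaries will include all AEs starting on or after study day 1" and then adds that they must be "ending no later than 28 days after last study treatment or the follow-up visit, whichever is later". The same section lists every AE before the data cutoff, including those with onset before day 1, and applies no end-date limit to the listings.

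**Dates.** On AE dates, SAP 6.3 says only: "The imputation of partial date for AE and concomitant medication will follow Novartis standard rules". It refers to a module that is not among the documents. It is about partial dates and does not mention events that have no end date.

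**Protocol.** Protocol 7.1 records for each AE "its duration (start and end dates or if continuing at final exam", and says that once detected "it should be followed until its resolution or until it is judged to be permanent". Protocol 7.2 sets its 28-day window for SAEs on occurrence: "occurring after the patient has provided informed consent and until 28 days after the patient has stopped study participation". Protocol 9.5.3 tabulates AEs by body system and preferred term with no end-date restriction.

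**Counting.** SAP 7.5.1 counts a patient once per body system only on condition that severity did not change. SAP 7.5.1.3 counts the patient once, and uses the maximum grade in the by-grade tables. Protocol 9.5.3 counts once with no condition.

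**The concern.** An incidence table answers how many patients developed an event during the risk period, so membership should depend on onset. Here the lower bound is on onset and the upper bound is on resolution. The events lost are those that resolve late and perhaps those that never resolve. These matter most in a report of which SAP 3 says: "The Final CSR will concentrate on reporting long-term safety and efficacy of osilodrostat".

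Such events are foreseeable. The protocol provides for AEs still continuing at the last examination and follows AEs to resolution or permanence. Under Protocol 6, patients moving to the roll-over study have no end-of-study visit because treatment is uninterrupted, so some AEs may well be open when they leave.

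If the rule is programmed literally, the tables understate incidence while the listings still show the events. Tables and listings already differ by design for events before day 1; this difference would be unintended and would concern events that began on treatment.

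The severity condition is a smaller matter. It leaves two counting rules in one SAP, though no inflation of rates is shown.

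**Working it through.** The plan states no figure for this point, so there is none to reproduce. The check applies the rule as written, compares it with an onset window, and then sizes the loss of one patient.

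**1. The two rules.** Let *s* be the AE start day, *e* its end day and *L* the limit.

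- As written: include if *s* ≥ 1 and *e* ≤ *L*.
- Onset window: include if *s* ≥ 1 and *s* ≤ *L*.

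Since *s* ≤ *e*, every event with *e* ≤ *L* also has *s* ≤ *L*. The literal set is contained in the onset set, so for the same limit the literal rule can lower an incidence but never raise it.

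**2. Example.** Assume the last dose is on day 154 (end of the core phase) and the follow-up visit on day 154 + 28 = 182, so *L* = 182. The events are invented.

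| AE | As written | Onset window |
|---|---|---|
| day 100 to 120 | in | in |
| day 150 to 181 | in | in |
| day 150 to 183 | **out** | in |
| day 150, ongoing | **undetermined** | in |
| day 190 to 195 | out | out |

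The second and third events start on the same treatment day and differ only in resolving two days apart, yet just one is counted. The fourth has no *e* to compare with *L*, and no supplied section says how to treat it.

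**3. Size per lost patient.** The All Patients column combines both cohorts (SAP 6). The Protocol Amendment 9 rationale gives 19 patients enrolled under Amendment 4; all 19 are assumed to be in the safety set. A patient leaves a term only if no other event of that term qualifies.

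- 1/19 = 5.3%, 2/19 = 10.5%, 3/19 = 15.8%, 4/19 = 21.1%.
- Expansion cohort at its planned size of 15: 1/15 = 6.7%.
- Follow-up cohort: its size is not given. If the expansion cohort took 14 to 16 of the 19 (assumption), 3 to 5 remain: 1/5 = 20.0%, 1/4 = 25.0%, 1/3 = 33.3%.

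**4. Registry table.** SAP 7.5.1.3 plans a table of "on-treatment adverse events which are not serious adverse events with an incidence greater than 5" per cent. One patient in 19 is 5.26%, just above the cut-off, so a single-patient term appears. Omit that patient and it is 0/19 = 0%, and the term disappears. This applies only if that table uses the same window, which the SAP does not say.

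**The case against.** The strongest reply is that the sentence was meant as a reporting window and would be programmed that way. The rest of the paragraph sorts events by start date, and Protocol 7.2 runs its window on occurrence. That is probably the intent, but in the sentence both participles attach to the AEs, and there is no noun such as period or window for the second to describe. A programmer following the SAP has no ground to read it otherwise.

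The clearly excluded group may also be small. The limit is the later of two dates, and an AE unresolved at the final visit may simply be recorded as continuing, which moves it from excluded to unspecified. The limit can also be read as 28 days after the later of last dose and follow-up visit. In the example that gives 182 + 28 = 210, and the event ending on day 183 would be kept. This narrows the problem without removing it: an event ending after day 210 is still lost, and an ongoing event still has no rule.

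The module cited in SAP 6.3 might deal with ongoing AEs. It cannot be checked here, and the SAP invokes it only for partial dates.

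Finally, the percentage-point figures are illustrations, since the documents do not show how many events would be affected. That is correct, and the conclusion does not depend on them.

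**Conclusion.** The concern holds. As written, the rule omits on-treatment AEs with a recorded end date past the limit and leaves ongoing AEs undecided. The bias is one-directional, toward lower incidence, and is confined to the summary tables. Its total size is unknown. Each patient lost from a term costs 5.3 points among 19 and 6.7 points in a cohort of 15. The cost would be 20 to 33 points in a follow-up cohort of 3 to 5, a size that is assumed. The registry effect is conditional on a shared window. The severity condition in SAP 7.5.1 is a plain inconsistency with SAP 7.5.1.3 and Protocol 9.5.3. Both points should be fixed before the tables are programmed.

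**What to change.** - **SAP 7.5.1.3, window:** define the summary set by onset alone, from study day 1 up to the existing upper limit. State that an AE is included whatever its end date and that ongoing AEs are included. While redrafting, make clear whether the 28 days run from the last dose only or also from the follow-up visit.
- **SAP 7.5.1.3, registry tables:** add one sentence saying whether on-treatment there means the same window.
- **SAP 7.5.1:** delete the condition on unchanged severity, so that each patient counts once per body system and once per preferred term, at maximum grade in the by-grade tables.

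The cost is two wording edits and one clarifying sentence, with no new data. Reported incidences may come out somewhat higher than under the literal rule.
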